6.3 Other Subject Data

Study subjects will be characterized by descriptive statistics for:

- Disposition of subjects;
- Protocol deviations;
- Demographics and other baseline characteristics;
- Medical history and concomitant diseases;
- Prior and concomitant therapies (medication, non-drug treatments, and procedures); and
- Extent of exposure.

[figure not shown]
Disposition of subjects, demographic data, and baseline characteristics will be presented using standard descriptive statistics. Demographic data will be summarized for SES, ITT, and PPS; disposition of subjects will be summarized based on all randomized subjects.

Disposition of subjects

The number of subjects screened will be provided. Other subject disposition (i.e., number of subjects randomized, column the number of subjects in each analysis population) will be summarized by treatment group and overall.
The absolute and relative frequencies for subject's main reason of premature discontinuation will be tabulated
Visit attendance CO
will be presented in a frequency table overall and for both
treatment groups.

[figure not shown]

Protocol deviation

All protocol deviations including minor protocol deviations will be listed.

[figure not shown]
Demographics and other baseline characteristics

Medical history and concomitant diseases

Separation of medical history from concomitant diseases will be done according to the stop date of the finding in comparison to start of study treatment. Each finding will be allocated unambiguously either to medical history or to concomitant diseases.

- Medical history: If stop date is before start of treatment.
- Concomitant disease: If the stop date is at or after start of treatment or ongoing (even if it refers to a cut-off point before start of treatment) is ticked.

Medical history and concomitant diseases will be described based on MedDRA SOC and PT levels for the SES.

Previous and concomitant medication CCI

Separation of previous from concomitant therapies will be done according to the start and stop date of the therapy in comparison to the date of first injection. Each therapy will be allocated unambiguously either to previous therapies or to concomitant therapies.

- Previous therapy: If stop date is before start of treatment.
- Concomitant therapy:
 - If the start date is at or after start of treatment, and/or
 - if the stop date is at or after start of treatment or ongoing is ticked.

CCI

Previous and concomitant medication will be coded by use of the World Health Organization Drug Dictionary (WHO-DD) whereby the version in effect at the time the respective database is closed will be used for interim and final analysis.

[figure not shown]
Frequencies of previous and concomitant medications will be given based on different Anatomical Therapeutic Chemical Classification system code levels of the World Health Organization (ATC) for the SES. Indications are taken into consideration to assign the appropriate ATC code when a drug is coded with WHO-DD, but will not be coded itself with MedDRA and only listed.

cci

Extent of exposure

[figure not shown]
Frequencies of subjects receiving treatment

will be summarized by treatment group for the SES.

6.4 Special Statistical/Analytical Issues

6.4.2 Interim Analyses

. Safety analyses will be performed on the SES. Effectiveness data will be analyzed on the ITT and PPS where applicable. The interim analysis is not proposed to modify the study design, statistical analyses, or sample size, or for study termination, as this is not an adaptive study design.

After the end of the safety follow-up the database until Week 84/cc will be closed and the data until Week will be analyzed. All tables and listings planned for the final analysis will also be done for the interim analysis cc

6.4.3 Multiple Comparisons/Multiplicity

Based on the primary effectiveness endpoint, two hypothesis tests will be performed. To control for multiplicity, a hierarchical-testing procedure will be performed (see Section 6.1.1).

8 References

[1] Ian R. White, Rhian Daniel, Patrick Royston (2010): Avoiding bias due to perfect prediction in multiple imputation of incomplete categorical variables. Comput Stat Data Anal. 2010 Oct 1;54(10):2267-2275. doi: 10.1016/j.csda.2010.04.005. PMID: 24748700; PMCID: PMC3990447.

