13.4.1 Effectiveness Analyses

13.4.1.1 Primary Effectiveness Endpoint

The primary effectiveness endpoint (Section 7.2.1.1) will be summarized as counts and percentages for the treatment and control groups.

Two hypothesis tests will be performed, based on the primary effectiveness endpoint. These tests will be evaluated in a sequential order on the ITT. To control for multiplicity, a hierarchical-testing procedure will be performed at a one-sided α level of 0.025.

The first hypothesis of the primary analysis is to demonstrate that the response rate is statistically significantly larger than 50% in treated subjects. This 50% threshold is commonly used in aesthetic medical device studies to measure a meaningful response.

The second hypothesis is to show statistical superiority of treatment over untreated control. Both hypotheses will be tested using the lower limits of the 95% CIs (two-sided), based on Wilson scores. The lower limit of the 95% Wilson CI must exceed the margin of 50% responder rate to reject Hypothesis 1 (H_{10}). The lower limit of the 95% Newcombe CI must be greater than zero to reject Hypothesis 2 (H_{20}).

13.4.1.1.1

[figure not shown]

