13.4.1.2 Secondary Effectiveness Endpoint

[figure not shown]
Treatment comparisons for the secondary effectiveness endpoint proportion of responders at Week 24 on MAS Décolleté Wrinkles Dynamic as assessed live by a blinded evaluator will be conducted analogous to the primary effectiveness endpoint. Descriptive two-sided 95% Wilson score based CIs, will be performed

The iGAIS and sGAIS assessments describing the overall impression of post-treatment aesthetic change specific to the décolleté compared to baseline photograph as well as percentage of subjects with improvement in iGAIS and sGAIS will be evaluated at Week 24 by baseline severity and in total.

13.4.1.3

[figure not shown]

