6.1.1.1 Primary analysis

The first hypothesis of the primary analysis is to demonstrate that the response rate Π_A at Week 24 is statistically significantly larger than 50% in treated subjects, i.e.,

 H_{10} : $\Pi_A \le 50 \%$ versus H_{11} : $\Pi_A > 50 \%$.

[figure not shown]
This 50% threshold is commonly used in aesthetic medical device studies to measure a meaningful response.

The second hypothesis is to show statistical superiority of treatment over untreated control. Superiority of treatment means that the response rate in the 'Treatment' group, Π_A , is statistically significantly larger than the response rate in the 'Control/Delayed treatment' group, Π_B , i.e.

 H_{20} : $\Pi_A \leq \Pi_B$ versus H_{21} : $\Pi_A > \Pi_B$.

Both hypotheses will be tested using the lower limits of the 95% CIs (two-sided), based on Wilson scores. The lower limit of the 95% Wilson CI must exceed the margin of 50% responder rate to reject the first Null hypothesis H_{10} . The lower limit of the 95% Newcombe CI for the difference between the responder rates in the 'Treatment' group and the 'Control/Delayed treatment' group $(\Pi_A - \Pi_B)$ must be greater than zero to reject the second Null hypothesis (H_{20}) .

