6.1.2 Secondary Effectiveness Endpoints

MAS Décolleté Wrinkles-Dynamic response

[figure not shown]
Treatment comparisons for the secondary effectiveness endpoint proportion of responders at Week 24 on MAS Décolleté Wrinkles Dynamic as assessed live by a blinded evaluator will be conducted analogous to the primary effectiveness endpoint. Descriptive two-sided 95% Wilson score-based

```
CIs, CCI will be performed CCI descriptive summary statistics. CCI
```

The Global Aesthetic Improvement Scale

The iGAIS and sGAIS assessments describing the overall impression of post-treatment aesthetic change specific to the décolleté compared to baseline photograph as well as percentage of subjects with improvement in iGAIS and sGAIS will be evaluated at Week 24 by baseline severity and in total for the 'Treatment' group.

For each GAIS category (i.e., -3 = very much worse, -2 = much worse, -1 = worse, 0 = no change, +1 = improved, +2 = much improved, +3 = very much improved), counts (n) and percentages (%) will be presented.

The Global Aesthetic Improvement Scale

[figure not shown]
The iGAIS and sGAIS assessments describing the overall impression of post-treatment aesthetic change specific to the décolleté compared to baseline photograph as well as percentage of subjects with improvement will be evaluated for each post-treatment follow-up visit (except Week 24) and by baseline severity and in total. For subjects receiving an optional retreatment at Week 36 in 'Treatment' group, an additional summary will be used to report iGAIS and sGAIS scores relative to the Week 36 reference photograph.

For each GAIS category (i.e., -3 = very much worse, -2 = much worse, -1 = worse, 0 = no change, +1 = improved, +2 = much improved, +3 = very much improved), counts (n) and percentages (%) will be presented by treatment group.

Additionally, iGAIS and sGAIS will be categorized in classes of "improvement" (scores +1 to +3) and "no improvement" (scores -3 to 0) and frequencies for these categories will be provided. Descriptive two-sided 95% Wilson CIs will be calculated for subjects with "improvement".

Moreover, metric descriptive summary statistics will be provided for the iGAIS and sGAIS by treatment group.

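### MAS-Dynamic is compared with control but sits outside the two-test hierarchy; adding it as a gated third step would allow an error-controlled conclusion at no alpha cost

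*SAP*

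**What the plan says.** **The hierarchy.** Protocol 13.4.1.1 says "Two hypothesis tests will be performed, based on the primary effectiveness endpoint" and "To control for multiplicity, a hierarchical-testing procedure will be performed at a one-sided α level of 0.025". SAP 6.4.3 repeats the count ("Based on the primary effectiveness endpoint, two hypothesis tests will be performed") and refers back only to Section 6.1.1. The two tests, called H1 and H2 here, are:

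- H1, Group A responder rate above 50%: "The lower limit of the 95% Wilson CI must exceed the margin of 50% responder rate to reject the first Null hypothesis" (SAP 6.1.1.1).
- H2, superiority over untreated control: "The lower limit of the 95% Newcombe CI must be greater than zero to reject Hypothesis 2" (Protocol 13.4.1.1).

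**MAS-Dynamic.** Protocol 13.4.1.2 and SAP 6.1.2 both address "Treatment comparisons for the secondary effectiveness endpoint proportion of responders at Week 24 on MAS Décolleté Wrinkles Dynamic", and the comparisons "will be conducted analogous to the primary effectiveness endpoint". The next sentence in each document calls the two-sided 95% Wilson-based intervals descriptive. No visible text gives MAS-Dynamic a place in the testing order or a share of alpha.

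**Standing among the secondaries.** SAP Table 1 gives MAS-Dynamic the same three analyses as the primary: ITT with multiple imputation, ITT observed cases, and PPS. It also shares the Week 24 time point, the live blinded rating and the 1-point response definition. The Week 24 GAIS endpoints are rated by the subject or the treating investigator with photographs (Protocol Table 1), have no imputed analysis, and are summarized for the Treatment group only (SAP 6.1.2).

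**The concern.** MAS-Dynamic has everything needed for a confirmatory comparison except a place in the sequence. The objective in Protocol 7.1 and SAP 2.2 is superiority in correcting décolleté wrinkles and is not confined to wrinkles at rest. As written, the blinded, randomized Dynamic comparison can yield only an estimate and an interval.

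The wording also leaves its status open. A comparison done like the primary suggests a decision rule; the descriptive label suggests none. The general rule in Protocol 13.4 and SAP 6, under which tests not otherwise specified run two-sided at 5%, adds to the doubt. At stake are an error-controlled second conclusion that could be had for nothing, and clarity about what a favourable Dynamic interval may be used to say.

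**Working it through.** **Inputs from the documents.** One-sided alpha 0.025; H1 margin 50% (Wilson); H2 margin 0 (Newcombe); 114 and 38 randomized (Protocol 13.1); 120 evaluable (Protocol 9.1), which is 90 and 30 if split 3:1. The rates and power behind the effectiveness sample size are blacked out, so every responder rate below is an assumption.

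**1. The plan's own figure.** The one stated probability with all inputs visible is the safety detection probability: 1 − 0.985^152 = 0.8995, against the stated 89.9%. It reproduces. The effectiveness sample size cannot be recomputed.

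**2. The decision rules.** With z = 1.96, the Wilson lower limit is [p + z²/(2n) − z√(p(1−p)/n + z²/(4n²))] / (1 + z²/n). At n = 114, H1 needs at least 68 responders (lower limit 0.505; 67 gives 0.496). Its exact size at a true rate of 50% is 0.0244. The Newcombe lower limit is (pA − pB) − √[(pA − lA)² + (uB − pB)²], where lA and uB are the Wilson lower limit in A and upper limit in B.

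**3. Cost of a third gated step.** Order the tests H1, H2, H3, with H3 being Dynamic superiority, each at one-sided 0.025 and each reached only if the previous null is rejected. A false rejection anywhere requires rejecting the first true null in the order, so nominal familywise error stays at 0.025. H1 and H2 are decided before H3 and do not change. In simulation (100,000 trials, 114/38, latent correlation 0, 0.5 and 0.8):

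- Group A At Rest rate 50%, so H1's null is true: familywise error 0.024 to 0.025.
- At Rest 70% vs 20%, Dynamic 20% vs 20%: false Dynamic claim 0.019.

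**4. What an ungated Dynamic test would do.** Two free-standing independent tests would give 1 − 0.975² = 4.94%. But H2 is not free-standing: it is reached only after H1. Let g be the exact probability, at 114/38 and equal At Rest rates in both groups, that H1 and H2 are both passed. With an independent 2.5% Dynamic test, the chance of at least one false superiority claim is 1 − (1 − g) × 0.975.

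| Common At Rest rate (assumed) | g | At least one false superiority claim |
|---|---|---|
| 10-40% | below 0.0001 | 2.5% |
| 50% | 0.0048 | 3.0% |
| 60% | 0.0248 | 4.9% |

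Positive correlation lowers these. Beyond 60% the gate has little effect and Newcombe's approximation matters: its exact size peaks at 0.032 near a common rate of 0.89, giving 1 − 0.968 × 0.975 = 5.6%. That excess already affects H2 and is not caused by adding H3. If a false H1 rejection at exactly 50% is also counted as an error, the simulated chance of any error is 4.5% to 4.7%; that is not a superiority claim.

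**5. Whether the step is worth having.** Power for Dynamic superiority alone:

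| Dynamic rates (assumed) | 114/38 | 90/30 |
|---|---|---|
| 40% vs 20% | 64% | 52% |
| 50% vs 20% | 93% | 86% |
| 40% vs 10% | 97% | 92% |

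Success is capped by the gate: at 114/38, H1 and H2 both pass with probability 90% at At Rest rates of 65% vs 20%, and 57% at 60% vs 10%.

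**6. The 50% test for Dynamic.** Following the primary exactly could also bring in a 50% threshold. With At Rest 70% vs 20% and Dynamic 60% vs 20%, the three-step chain passes about 99% of the time; requiring the Dynamic 50% threshold as well cuts this to about 57%.

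**The case against.** A controlled primary family with descriptive secondaries is coherent and common. The sponsor may choose not to seek a confirmatory secondary conclusion, and the objective does not require one: At Rest is the designated primary measure and also defines baseline severity (SAP 6). All of that stands, so the gap is not an error.

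A reader might infer that the plan will make an uncontrolled Dynamic superiority claim, or that it carries a 4.9% familywise error. The documents support neither. No visible passage announces such a claim, and the intervals are labelled descriptive. The 4.9% ignores the H1 gate: for false superiority claims it arises only if around 60% or more of untreated women would count as responders. Independence is also unlikely, since both scales are rated live by a blinded evaluator in the same subjects at the same visit.

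Text around the Dynamic analysis is blacked out in both documents, as are the sample-size assumptions, so the power for H3 is unknown. The statements that the hierarchy has two tests are intact in both, and the finding rests on those.

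Finally, a third step is free only if the order is set before the Week 24 data are analysed. That is correct and belongs in the fix.

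**Conclusion.** The point holds as a free improvement and a clarification. The error-controlled hierarchy covers At Rest only; MAS-Dynamic, the one secondary effectiveness endpoint with a planned blinded, randomized comparison, supports no superiority conclusion with type I error control. Its estimate and interval can still be reported. Nothing here weakens H1 or H2.

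Gating Dynamic superiority behind both keeps nominal familywise error at one-sided 2.5%, provided the order is fixed in advance. Nominal is the right word, because the Newcombe rule is approximate. The probabilities of false claims and of success rest on assumed rates, since the documents show none.

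**What to change.** In SAP 6.4.3 and 6.1.2 and in Protocol 13.4.1:

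1. Add H3: the Week 24 MAS-Dynamic responder rate is greater in Treatment than in Control. Use the same ITT data with multiple imputation, require the lower limit of the two-sided 95% Newcombe interval to exceed zero, and test only if H1 and H2 are both rejected.
2. Fix this order before any Week 24 data are analysed. The opening section of the SAP already requires it to be final before the interim analysis.
3. State that any 50% threshold for Dynamic is descriptive and does not precede H3.
4. Keep the remaining secondary endpoints descriptive.

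If the sponsor prefers not to add H3, replace the reference to the primary with a plain statement that the Dynamic comparison is descriptive and supports no superiority claim.

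The cost is wording in two documents, with no extra subjects, data or alpha. If Week 24 data have already been analysed, which the documents do not show, H3 can no longer be added as a prespecified test and only the clarification remains.
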